## 8. Data Collection/ Study Measures

### **Assessment Measures**

**Assessors:** Assessors will be masked to treatment assignment of participants. Assessors are located at the JP campus of VA Boston. Participants will have the option of conducting assessment sessions in person at the JP campus or via telephone. For participants opting to conduct assessments via telephone, self-report measures will be mailed to them in advance of the clinician-administered assessment, and participants will be asked to return completed self-report

measures within two weeks in a self-addressed stamped envelope that will be provided to them. Assessments conducted for the other recruitment sites in the study (e.g., Madison, WI and Charleston, SC) will all be conducted via telephone with self-report measures collected at the recruitment sites.

**Structured Clinical Interview for DSM-5** (SCID-5; First et al., 2015): The SCID-5 includes questions assessing each of the DSM-5 adult disorders (Spitzer, et al., 1994). Each disorder is coded as present, not present, or probable, based on structured questions that map onto the DSM-IV criteria. Additionally, each diagnosis will be given a Clinical Severity Rating (CSR) of 0 to 8, where a rating of 4 or higher represents clinical levels of interference or distress. Individuals receiving a CSR of 4 or higher for substance dependence disorders or bipolar disorder or reporting any psychotic symptoms will be excluded.

**Structured Clinical Interview for DSM-5 Personality Disorders, Borderline module only** (SCID-5-PD; First, Williams, Benjamin, & Spitzer, 2016). The SCID-5-PD is a semi-structured diagnostic interview assessing DSM-5 personality disorders using the same coding strategy as described above for the SCID-5. Clinicians will only administer the Borderline Personality Disorder (BPD) section of the SCID-5-PD at each assessment occasion to measure the presence of BPD diagnoses or traits at baseline assessment.

Frequency and quantity of alcohol and substance use will be assessed using clinician-administered measures adapted from the PhenX Toolkit (version June 4, 2019, Ver 26.0). These measures were derived from reliable and valid measures of alcohol and substance use and selected based on scientific community consensus (Hamilton et al., 2011). Specifically, the **Alcohol – 30-Day Quantity and Frequency** is a 2-item measure that assesses the quantity and frequency of alcohol consumption during the past 30 days. The **Substance Use Frequency** measures assess the use of ten categories of substances (including prescription drug misuse) over the past 30 days. This scale also includes an item assessing average quantity of cannabis use episodes per day in the past 30 days. All three of these measures will be administered by clinicians at each assessment occasion in order to examine changes in alcohol and substance use during treatment.

**The Clinician Administered PTSD Scale for DSM-5** (CAPS-5; Weathers et al., 2013a). The CAPS-5 is a structured diagnostic interview and the gold standard for assessing the DSM-5 symptoms of PTSD (American Psychiatric Association, 2013). The scale also assesses social and occupational functioning, dissociation symptoms, and the validity of symptom reports. The CAPS-5 uses a single 5-point ordinal rating scale to measure symptom severity. Symptom severity ratings combine information about symptom frequency and intensity obtained by the interviewer. Psychometric properties indicate high criterion and construct validity and high agreement with a self-report measure of PTSD (Weathers et al., 2018). The CAPS-5 requires approximately 40 minutes to administer. Participants' total CAPS-5 severity scores will serve as the primary outcome of interest.

**Life Events Checklist-5 (LEC-5).** The LEC-5 (Weathers, Blake, Schnurr, Kaloupek, Marx, & Keane, 2013) will be used to determine the presence of a traumatic life event(s). The LEC-5 includes the same list of 16 different potentially traumatic events (PTE) from the original LEC and is designed to facilitate PTSD diagnosis (Weathers et al., 2013). For each PTE, respondents rate their

experience of that event on a 6-point nominal scale. There are no published data on the psychometric properties of the LEC-5, but is nearly identical to the original LEC, which has high internal consistency and test-retest reliability (Weathers et al., 2013). The worst traumatic event identified at the initial assessment is recorded and used for all subsequent administrations of the CAPS-5. The LEC-5 requires approximately 15 minutes to complete.

The **World Health Organization Quality of Life BREF** (WHOQOL-BREF; WHO, 1998) instrument comprises 26 items, which measure the following broad domains: physical health, psychological health, social relationships, and environment. The WHOQOL-BREF is a shorter version of the original instrument that is more convenient for use in large research studies or clinical trials. This measure requires 5-10 minutes to complete. It is included in this study to examine quality of life improvement as a secondary outcome measure.

The **Personality Inventory for DSM-5 – Brief Form** (PID-5-BF; American Psychological Association, 2013) is a 25-item self-report measure that assesses five personality trait domains associated with personality dysfunction: negative affect, detachment, antagonism, disinhibition, and psychotism. The PID-5-BF will be administered at each assessment occasion to measure changes in maladaptive personality dimensions as a result of treatment.

**Multidimensional Scale of Perceived Social Support** (MSPPS; Zimet, Dahlem, Zimet & Farley, 1988) is a 12 item self-report measure of social support. Social support has been found to moderate outcome following a traumatic event. This measure will be included at baseline assessment to examine if social support moderates treatment outcome. In addition, the MSPPS will be administered at each assessment occasion to measure changes in perceived social support during treatment.

**Test of Premorbid Functioning** (TOPF) is a premorbid estimate of intelligence that takes 5-10 minutes to administer and requires participants to read a list of up to 70 words. This measure will be administered at baseline. In our prior non-inferiority study we found estimated IQ served as a moderator for CPT treatment outcome (with higher IQ predicting better outcome) but estimated IQ did not serve as a moderator for WET (Marx et al., 2017).

**Peritraumatic Dissociative Experiences Questionnaire** (PDEQ; Mamar et al., 1994) is a 10 item self-report measure of dissociative experiences during and immediately following a traumatic event. We will examine whether PDEQ moderates treatment outcome. This measure will be completed at each assessment occasion.

**Posttraumatic Cognitions Inventory** (PTCI-9; Wells et al., 2017) is a 9-item self report measure indexing cognitions following a traumatic event, such as self-blame and negative world cognitions. This measure will be completed at each assessment occasion to examine changes in posttraumatic cognitions as a result of treatment.

The **Openness to Sharing Questionnaire** (OSQ) is a 5-item self-report measure to assess the amount, depth, extent, detail, and difficulty of past disclosure related to a traumatic event. The first two items assess the respondent's amount and depth of disclosure (e.g., "How many times have you talked about this event?") and require a numerical response. The last three items (e.g.,

“When you talk about this event, how much detail do you include?) are rated on a standardized 7-point Likert scale. The measure is administered at baseline and all subsequent assessment timepoints; however, the questions at subsequent timepoints have been modified to explicitly assess disclosure outside of therapy or assessment sessions. The measure was developed by Bedard-Gilligan and colleagues (2012); however, psychometric properties are not published. This measure will be administered at each assessment occasion.

The **Family Involvement Questionnaire (FIQ)** is a self-report measure designed to assess preferences for and beliefs about interpersonal involvement in mental health treatment. The baseline version of the questionnaire includes six items, and the version for subsequent assessment points includes three items. Questions regarding openness/willingness for family involvement are rated on a 10-point Likert scale ranging from 1 (*Completely closed/unwilling*) to 10 (*Completely open/willing*). In a “check all that apply” format, participants are also asked to indicate who they would include in treatment, goals for interpersonal involvement, and concerns about interpersonal involvement. This measure will be administered at each assessment occasion.

The **Insomnia Severity Index (ISI)** is a brief (7 item) instrument that was designed to assess the severity of both nighttime and daytime components of insomnia. It is increasingly used as a metric of treatment response in clinical research and will be used in the current study to assess changes in insomnia symptoms as a function of treatment. This measure will be administered at each assessment occasion.

#### *Safety Monitoring Measures*

The **PTSD Checklist for DSM-5 (PCL-5)** (Weathers, Litz, et al., 2013) will be administered at each assessment occasion, including baseline, and the beginning of every treatment session to monitor for symptom worsening, defined as an increase from the initial assessment of at least 10 points that is sustained for at least three consecutive treatment sessions (Foa, Zoellner, Feeny, Hembree, & Alvarez-Conrad, 2002). The PCL-5 is completed in reference to the identified criterion A event established at the baseline assessment. This is a psychometrically strong measure that is sensitive to change (Weathers et al., 2013; Bovin et al., 2016) and requires no more than 5-10 minutes to complete.

The **Beck Depression Inventory-II (BDI-II)** (Beck et al., 1996) is a 21-item self-report measure assessing current depressive symptoms and has well-established reliability and validity (Dosois et al., 1998). The BDI-II will be administered at each assessment occasion, including baseline, and the beginning of every treatment session to monitor exacerbation of depression symptoms associated with treatment, as well as to assess any changes in suicidal ideation. This measure requires no more than 5-10 minutes to complete.

The **Self-Injurious Thoughts and Behaviors Interview (SITBI)** (Nock et al., 2007) is a structured clinical interview that assesses the presence, frequency, and characteristics of a wide range of self-injurious thoughts and behaviors, including suicidal ideation, suicide plans, suicide gestures,

suicide attempts, and nonsuicidal self-injury. The SITBI has demonstrated excellent psychometric properties in multiple samples, including strong interrater reliability, and test-retest reliability over a 6-month period. Moreover, concurrent validity was demonstrated via strong correspondence between the SITBI and other measures of suicidal ideation, suicide attempt, and nonsuicidal self-injury. This interview takes approximately 20 minutes to administer.

#### *Therapy Process Measures*

The **Treatment Expectancy Questionnaire (TEQ)** is a widely-used measure of treatment credibility (Borkovec & Nau, 1972). This measure is administered at the conclusion of the first treatment session (after the treatment rationale and specific procedures are explained). The TEQ asks the individual to rate on a 10-point scale how logical the treatment seems, the participant's confidence in undergoing the treatment and recommending it to others, and their expectations for the treatment's success. We anticipate treatment expectancy to be high for both treatments, with no significant between condition effects. The measure requires approximately 5 minutes to complete.

The **Client Satisfaction Questionnaire (CSQ; Larsen, Attkisson, Hargreaves, & Nguyen, 1979)**, a measure of participant satisfaction with treatment, is administered at the last treatment session. This 8-item measure assesses satisfaction with treatment and has demonstrated concurrent validity. We expect client satisfaction ratings to be high for both conditions. The measure requires approximately 5 minutes to complete.

The therapeutic alliance will be assessed using the 12-item therapist and client versions of the **Working Alliance Inventory (WAI; Horvath & Greenberg, 1989; Tracey & Kokotovic, 1989)**. In addition to the total score, the WAI has three subscales: Goals, which reflects the agreement between therapist and patient on overall goals of treatment; Tasks, which reflects the agreement on the appropriate tasks on which to focus (to achieve goals); and Bond, the quality of the affective relationship between the therapist and the patient. The WIA will be included to examine therapeutic alliance as a potential moderator of treatment outcome, as well as to examine potential treatment condition differences. The WAI therapist version will be completed by the study therapists for each participant they treat, and the client version will be completed by each participant enrolled in the RCT at the end of treatment.

In the PE condition, clinicians will complete Homework Review Forms (HRFs) specific to PE session content to assess homework compliance. There is no homework in the WET condition.

**Table of Assessment Schedule**

Measure	Baseline	First Tx Session	Weekly During Tx	Last Tx Session	10-week	20-week	30-week
LEC-5	X						
TOPF	X						
SCID-5	X						
SCID-5-PD BPD only	X						
CAPS-5	X				X	X	X
SITBI	X		if needed		X	X	X
Alcohol 30-day	X				X	X	X
Substance Use Frequency	X				X	X	X
PID-5-BF	X				X	X	X
MSPPS	X				X	X	X
WHOQOL-BREF	X				X	X	X
PDEQ	X				X	X	X
OSQ	X				X	X	X
FIQ	X				X	X	X
ISI	X				X	X	X
TEQ		X					
PCL-5	X		X		X	X	X
BDI	X		X		X	X	X
PTCI-9	X		X		X	X	X
CSQ				X			
WAI				X			

## INTERVENTIONS

**Written Exposure Therapy (WET).** The WET condition consists of 5 weekly treatment sessions, with the first session lasting 1 hour and each subsequent session lasting approximately 40 minutes. The first session consists of education about common trauma reactions and the WET rationale. The participant is then given general instructions for completing the trauma narratives and specific instructions for completing the first 30-minute narrative writing session. All WET sessions begin with the therapist reading the specific writing instructions, clarifying any questions the person has, and leaving the instructions with the participant during the 30-minute writing session. Writing instructions begin with a focus on the details of the trauma and then shift to the meaning of the trauma event. After 30 minutes of writing, the therapist stops the writing and conducts a 5-10 minute check-in regarding how the writing session went for the participant. In

response to VA clinician feedback indicating that veterans sometimes avoid writing about traumatic event in the first and sometimes second writing session, we will permit up to an additional two sessions to course correct in such situations. Specifically, if the veteran does not follow writing instructions in the first and/or second session, these sessions should be repeated to allow for necessary level of exposure to the traumatic event. However, additional sessions will not be provided even if patients continue to partially or fully avoid (i.e. do not follow writing instructions).

**Prolonged Exposure (PE).** PE is designed to be delivered in weekly 90 minute sessions over 8-15 sessions. The sessions are flexible according to the response of the patient. Stopping before 15 sessions should occur because (1) the patient has a stable score (i.e., at least two consecutive sessions) below the probable PTSD diagnosis cut score of 33 (Bovin et al., 2016) and (2) the clinician and patient agree that substantial clinical gain has occurred and no additional sessions are needed. Up to 15 sessions are provided if the score remains above the probable PTSD cut score. Treatment response is determined based on PCL-5 measure administered at each treatment session. The conceptual foundation of PE is based upon emotional processing theory (Foa & Kozak, 1986). The PE model proposes that chronic PTSD develops when there is a failure to process the traumatic memory because of extensive avoidance of trauma reminders. PE mimics the natural fear modification process. During PE, patients are encouraged to confront (or expose themselves) to safe but anxiety-eliciting situations, in both imagination and *in vivo*, with the goal of overcoming excessive fear and anxiety. Thus, PE includes the following core components: (a) psychoeducation about the common reactions to traumatic events and presentation of the rationale for PE, (b) repeated *in vivo* exposure to situations or objects being avoided due to distress and anxiety, and (c) repeated, prolonged imaginal exposure to memories of the event(s). The focus of treatment initially lies in educating the patient about the PTSD diagnosis, gathering of detailed information about the traumatic event, and providing a sound rationale for PE. Patients' understanding of the rationale for PE is important because recognition of the importance of breaking their patterns of avoidance is a key goal. Patients, together with their therapist develop a hierarchy of feared but safe trauma related situations and objects and are instructed to gradually approach these situations between sessions (*in vivo* exposure exercises). The structure of gradual exposure is fairly consistent with traditional exposure-based interventions such that anxiety-provoking stimuli (e.g., physical or verbal cues) are presented gradually. The 3rd component of treatment is imaginal exposure. During this phase, therapists assist patients in repeatedly recounting their traumatic event in detail, including their thoughts, feelings, and reactions that occurred during the event(s). Imaginal exposure is conducted during sessions and is audiotaped for patients to listen to at home between sessions.

## 9. Statistical Analysis Plan

Data will be analyzed in SPSS and MPlus software, which licenses are obtained by the Behavioral Science Division of the National Center for PTSD at VA Boston. The software is stored on a password protected server that is behind the VA firewall.

The equivalence of the treatment conditions will first be assessed according to key baseline variables (demographics and outcome variables) using t-tests, nonparametric equivalence, or Chi-square tests, depending on the type (continuous or dichotomous) and distribution (normal or

non-normal) of the data. Any variables that differ among groups will be used as covariates in the final analyses.

We anticipate some participant attrition during the trial. If a subject drops out of the study for any reason, we will vigorously pursue follow-up to minimize missing data. Yet, some data will inevitably be missing. Missing data will be handled in all analyses using direct maximum likelihood or multiple imputation techniques within MPlus 8.0 (Muthén & Muthén, 2018) under a missing at random (MAR) assumption. Modern missing data techniques such as direct ML increase statistical power and provide more accurate estimates of model parameters and standard errors, and are the recommended intent-to-treat approach for clinical trials (Enders, 2010). The primary analyses in this study will be performed on the intent-to-treat population that includes all patients randomized to a condition. Supplementary analyses will also be conducted examining outcomes in the subset of participants who complete a full course of treatment in each condition. In order to better understand the potential reproducibility of our findings, our conclusions from all analyses will be based on both the statistical significance of parameters and the magnitude of associated effect sizes.

**Aim 1.** Our primary hypothesis that WET will be non-inferior to PE will be evaluated using similar analytic procedures conducted in our previous non-inferiority trial of WET (Sloan et al., 2018). Specifically, the non-inferiority margin of 10 will be used for comparing the two conditions on the primary PTSD outcome of CAPS-5 scores at the 10 week, 20 week, and 30 week assessments. The mean difference score between conditions will be calculated at each follow-up and the hypothesis of non-inferiority will be evaluated based on whether the entire 95% confidence interval of the mean difference is less than the margin of 10 points. We will then supplement this analysis by calculating additional effect sizes to characterize between condition differences in PTSD outcomes. Specifically, we will calculate Cohen's  $d$  (with 95% CI) for the mean difference in CAPS-5 scores at each time point and will calculate odds ratios (with 95% CI) for the proportion of participants who no longer meet diagnostic criteria for PTSD based on the CAPS-5 at each assessment period.

**Aim 2.** The comparison of treatment dropout in WET vs PE will be examined by calculating odds ratio effect sizes (with 95% confidence interval) for the proportion of participants who do not complete a full course of treatment (5 sessions) in WET and those who drop out of PE by session 5. The statistical significance of the between-group differences in dropout rates will then be evaluated using a chi-square difference test.

**Aim 3.** The exploratory analyses of moderators of WET and PE will be conducted using latent growth curve modeling conducted within Mplus. As the focus is not primarily on the nature of the growth trajectory, the intercept of the LGM will be centered on the baseline CAPS-5 assessment (i.e., first slope loading fixed to 0), the slope loading for the final time point will be fixed at 1.0, and loadings for all intermediate assessments will be freely estimated. The mean and variance of the slope factor in this model will reflect the total change in and individual differences in change

in PTSD symptoms across the full assessment period. The hypothesized moderators (age, sex, combat era, social support, time since index trauma event, and estimated IQ) will then be specified as predictors of the slope factor in separate models. These LGM will be conducted for the full sample first, and will then be conducted separately within each treatment condition to examine whether moderators of treatment outcome are consistent across WET and PE. To aid in the interpretation of clinical significance, results from LGM analyses will be converted to effect size metrics within 95% confidence intervals following established procedures (Feingold, 2015). Evaluation of model fit in the LGM models will be examined using fit diagnostics (i.e., standardized residuals) and common fit statistics (i.e., root mean square error of approximation) following the associated cutoff criteria recommended by Hu & Bentler (1999).

We will conduct additional exploratory analyses to evaluate characteristics of patients who require additional WET sessions, as well as characteristics of patients who require more than 12 PE sessions. These analyses will be conducted using logistic regression with dependent variable being more than 12 sessions of PE or more than 5 sessions of WET (conducted separately for each treatment condition). We will include characteristics such as age, time since trauma event, combat era, baseline PTSD symptom severity, baseline depression, baseline social support, baseline estimated IQ.

**Aim 4:** Follow standard practice for examining secondary outcome measures in a non-inferiority trial (e.g., Thompson-Hollands et al., 2018), we will use hierarchical linear modeling (HLM; Raudenbush & Bryk, 2002) to determine impact of treatment on functional impairment as measured by the WHOQOL-BREF. Analyses will be conducted using an autoregressive covariance matrix at level 1 (within person) and a scaled identity matrix at level 2 (between persons). A between-treatments variable will be included in the analysis, as functional impairment is a secondary outcome and therefore not subject to the same noninferiority analyses. Guidelines from Cohen (1988) will be used to interpret the within- and between-condition effect sizes ( $d$ ).

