## 2. Aims/Objectives

The proposed study will examine the extent to which WET is non-inferior in reducing PTSD symptom severity among veterans with PTSD relative to the widely used but more time intensive, PE.

We propose the following aims and hypotheses:

**Aim 1:** Determine if WET is non-inferior relative to PE in terms of PTSD symptom severity.

**Hypothesis 1a.** WET will be non-inferior to PE at both 10- and 20-weeks after initiating treatment. PTSD symptom severity will be assessed using the Clinician Administered PTSD Scale for DSM-5.

**Hypothesis 1b.** Non-inferiority will be maintained 30 weeks after initiating treatment.

**Aim 2.** Determine if WET has better treatment retention than PE.

**Hypothesis 2a.** WET will have significant fewer treatment dropouts compared with the first 5 sessions of PE.

**Aim 3:** We will explore potential moderators of treatment effects for both WET and PE. Given that prior studies of PTSD treatment moderators have shown mixed results, this aim is exploratory. Our exploratory analyses will include variables that have been tested in other studies (e.g., age, sex, combat era, pre-treatment depression, social support, and estimated IQ).

**Aim 4:** Functioning will be examined as a secondary outcome.

Hypothesis: We expect that participants assigned to both PE and WET will display significant improvements in functioning as measures by the WHOQOL-BREF, however, we do not expect to find between condition differences.

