## 6. Study Design

The proposed study will use a non-inferiority design to examine whether WET is non-inferior to Prolonged Exposure (PE), a first-line treatment for PTSD that is frequently used by VA treatment providers and is more time intensive.

The study will take place at three sites: VA Boston Healthcare System (VABHS), which has two PTSD clinic (PTC) clinics (Jamaica Plain and Brockton campuses), Ralph H Johnson (RHJ) VAMC PTC clinic, in Charleston, South Carolina, and William S. Middleton Memorial Veterans Hospital, Madison, WI. Veterans will be randomly assigned to either WET ( $n = 90$ ) or PE ( $n = 90$ ). Assessments will be conducted at baseline, and 10-, 20-, and 30- weeks post first treatment session. PTSD symptom severity, acquired through the use of a clinician-administered structured interview, will serve as the primary outcome variable.

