### **Randomization and Blinding**

After eligibility is determined, the project statistician, who is not involved in evaluations, will randomize participants using a computerized block (gender) randomization procedure with a 1:1 allocation ratio for WET and PE conditions. The project coordinator, who will be responsible for final determination of study eligibility, will be blinded to the randomization sequence. Participants will be unaware of study hypotheses and will be instructed not to reveal their randomization status to the IEs prior to each assessment. To further protect blinding, IEs will be located separately from the therapists, and a new rater will be assigned in the event of an unintentional unblinding.

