### Ethical Issues

#### a. Risks

There is a potential risk of loss of confidentiality for providers. While we will not be asking about sensitive personal information, providers may nevertheless describe opinions that could be perceived as critical regarding a given treatment. All data will be coded with a study ID number rather than the providers name, and transcripts will have identifying information removed (e.g., any proper names used by the provider will be replaced with a label indicating the role of that person,

such as [*the veteran*] or [*my coworker*]; the name of the facility/clinic will likewise be replaced by a label such as [*this facility*] or [*this clinic*]).

b. Potential Benefits

No anticipated direct benefits to providers.

1.

c. Analysis of Risks in Relation to Benefits

The risk of loss of confidentiality is low, and is balanced by the potential value of the information to be gathered. Any individual provider may choose not to share opinions or experiences that they feel are too sensitive to disclose, and they will be permitted to decline to answer any question at their own discretion.

d. Stopping Rules

A provider may always withdraw their participation at any time..

7. Study Subject Selection

a. Sample Description

Men and women veterans presenting to VA for mental health treatment services.

2.

b. Subject Inclusion Criteria

a current DSM-5 diagnosis of PTSD (assessed with the Clinician Administered PTSD Scale for DSM-5; CAPS-5),

veteran status

if taking psychotropic medication, on a stable dose for at least 30 days prior to study entry

c. Subject Exclusion Criteria

current engagement psychosocial treatment for PTSD,

current diagnosis of severe substance use disorder (mild to moderate severity will not be excluded; determined with SCID),

current psychosis or unstable bipolar disorder diagnosis (determined with MINI clinician-administered interview),

high suicidal risk (i.e., intent with a plan; assessed with the SITBI),

significant cognitive impairment (assessed with clinical judgement).

d. Recruitment

The primary recruitment strategy will be referrals by mental health providers in the PTC. In addition, we will notify additional mental health clinics about our study and seek referrals from these clinics as well (e.g., General Mental Health, Substance use clinics, Center for Returning Veterans, Behavioral Medicine). Given the study is now being conducted fully remotely due to

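### Aim 1 names no covariate and picks adjusters by baseline significance tests, so baseline CAPS-5 is usually omitted and the interval set against the margin is wider than it needs to be

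*Combined protocol and SAP*

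**What the plan says.** Under Aim 1 in Section 9, "The mean difference score between conditions will be calculated at each follow-up", and WET is non-inferior at a visit if the whole 95% confidence interval lies below 10 CAPS-5 points. The visits are 10, 20 and 30 weeks. No model and no covariate is named.

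The only text on adjustment is earlier in Section 9. Demographics and outcome variables are compared between arms at baseline with t-tests, nonparametric tests or chi-square tests, and then "Any variables that differ among groups will be used as covariates in the final analyses". No significance level is given for deciding that a variable differs.

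Other parts of the document bear on this:
- The CAPS-5 total is the primary outcome (Section 8). Section 7 also requires "a current DSM-5 diagnosis of PTSD (assessed with the Clinician Administered PTSD Scale for DSM-5; CAPS-5") for entry, so each randomised veteran should have a baseline score.
- Allocation uses a "computerized block (gender) randomization procedure with a 1:1 allocation ratio for WET and PE conditions" (Section 6). It does not balance baseline CAPS-5.
- In the Aim 3 growth model "the intercept of the LGM will be centered on the baseline CAPS-5 assessment", so baseline severity is built into an exploratory analysis but not into the primary one.
- Hypothesis 1a states that "WET will be non-inferior to PE at both 10- and 20-weeks after initiating treatment".

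**The concern.** In a randomised trial, a baseline difference between arms is due to chance. A test of that difference says nothing about whether the variable predicts outcome, and prediction of outcome is what makes a covariate worth including. Baseline CAPS-5 is likely to be among the strongest available predictors of follow-up CAPS-5, yet under this rule it is used only when the arms happen to differ on it.

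At stake is the width of the interval compared with the margin. If WET is somewhat worse than PE but inside the margin, or if fewer patients are analysed than planned, an unnecessarily wide interval makes an inconclusive result more likely. Hypothesis 1a needs success at two visits, so the loss counts at both.

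The rule is fixed in advance and uses baseline data only, so outcomes cannot steer it. Even so, chance decides which covariates the primary model contains.

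**Working it through.** **Inputs from the documents.** 90 per arm; margin 10; two-sided 95% interval (one-sided 0.025); success required at both 10 and 20 weeks.

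**Inputs not in the documents (assumed).** Follow-up SD 13 (also 11 and 15); baseline/follow-up correlation r of 0.3, 0.5 and 0.6; baseline tests at two-sided 0.05; correlation of 0.7 between the 10- and 20-week scores.

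**The plan's own figure.** Only the 90 per arm is stated, with no SD, power, true difference or dropout rate, so it cannot be reproduced. Working backwards from n = 2·SD²·(1.96 + z)²/10², with a true difference of 0 and no dropout, 90 per arm gives 80% power at SD = √(9000/(2 × 2.80²)) ≈ 23.9, and 90% power at SD ≈ 20.7.

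**How often baseline CAPS-5 is used.** A 0.05-level test of a chance difference is positive in 5% of trials; simulation gave 4.7–5.2%. It is therefore left out in about 95% (about 90% if the level were 0.10).

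**Closed form.**
- Unadjusted half-width: 1.96 × 13 × √(2/90) = 3.80.
- Adjusted for baseline: multiply by √(1 − r²), that is by 0.954, 0.866 or 0.800, giving 3.62, 3.29 or 3.04.
- Power at one visit: Φ((10 − δ)/SE − 1.96). For δ = 5, unadjusted SE = 13 × √(2/90) = 1.938, so Φ(0.62) = 73%. Adjusted at r = 0.5, SE = 1.678, so Φ(1.02) = 85%.

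**Simulation of the rule as written.** There were 40,000 trials per cell. Baseline CAPS-5 was t-tested at 0.05; ANCOVA was used if significant, and the raw difference otherwise. The comparator was ANCOVA every time. Success meant an upper 95% limit below 10. Baseline CAPS-5 was the only candidate covariate, and data were complete among those analysed.

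| SD 13 | r = 0.3 | r = 0.5 | r = 0.6 |
|---|---|---|---|
| Mean half-width, rule | 3.81 | 3.80 | 3.79 |
| Mean half-width, always adjusted | 3.65 | 3.32 | 3.06 |
| One visit, δ = 5, rule | 73–74% | 73–74% | 73–74% |
| One visit, δ = 5, always adjusted | 77% | 84% | 89% |
| Both visits, δ = 5, rule | 62% | 63% | 64% |
| Both visits, δ = 5, always adjusted | 66% | 76% | 82% |
| Both visits, δ = 3, 60 per arm, rule | 76% | 77% | 77% |
| Both visits, δ = 3, 60 per arm, always adjusted | 79% | 87% | 92% |

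Rows without a stated sample size use 90 per arm.

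- At δ = 0, power per visit is about 100% either way. At δ = 3 it is 95–96% under the rule against 96, 99 and 99%.
- With SD 11, one-visit power at δ = 5 is 86–87% under the rule against 89–97%. With SD 15 it is 61–62% against 64–79%.
- At a true difference of 10, false non-inferiority is 2.1–2.5% under the rule and 2.5–2.6% adjusted. The rule is slightly conservative because it corrects the trials with the largest baseline imbalance, while the intervals of the rest still allow for such imbalance.

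**Check at another SD.** With SD 12 and r of 0.3, 0.5 and 0.7 (20,000 trials each), the mean half-width is 3.52, 3.50 and 3.48 under the rule against 3.37, 3.06 and 2.52. The rule recovers almost none of the available gain.

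**The case against.** - **The earlier trial's methods.** Aim 1 says it will follow procedures similar to those of the previous non-inferiority trial of WET, and those may have modelled baseline. They are not in the documents and cannot be checked. The procedure that the SAP does spell out names no covariate.
- **Change scores.** The phrase "The mean difference score between conditions will be calculated at each follow-up" could mean change from baseline, which always uses the baseline value. With equal SDs of 13 the change-score half-widths are 4.52, 3.82 and 3.42 at r = 0.3, 0.5 and 0.6, still wider than ANCOVA. If the entry criterion narrows the baseline spread (assumed baseline SD 9, follow-up SD 13), they are 3.94, 3.39 and 3.08 against 3.66, 3.32 and 3.07, so the loss nearly vanishes at the two higher correlations. The plain reading is follow-up scores at each visit, but the ambiguity is real and is itself a reason to name the model.
- **Missing data.** The SAP analyses everyone randomised by direct maximum likelihood or multiple imputation, so the 60-per-arm complete-case figures probably understate the plan. If baseline is in that model, which is not stated, then with 60 of 90 observed the variance falls by r²/3, about 3, 8 or 12%. That recovers only part of the loss. With complete data and freely estimated baseline means, the likelihood contrast at follow-up is the unadjusted one.
- **Size.** The large gaps need a correlation of at least 0.5 and WET truly 3 to 5 points worse. Nothing in the documents anticipates a 5-point deficit. Restricting entry to diagnosed patients may also lower the correlation. This stands, and it limits how much weight the point carries.

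**Conclusion.** The concern holds. As written, baseline CAPS-5 enters the primary comparison only if the arms happen to differ on it, about 1 trial in 20 at an assumed 0.05 level. At SD 13 and 90 per arm, the half-width given up is 3.81 − 3.65 = 0.16 points at r = 0.3 (small), 3.80 − 3.32 = 0.48 at 0.5 and 3.79 − 3.06 = 0.73 at 0.6. The effect on the conclusion is negligible if the treatments are equal. It becomes material if WET is several points worse within the margin, if the SD is high, or if attrition is heavy.

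This is a loss of efficiency. It does not bias the comparison or make a false claim of non-inferiority more likely. It should be fixed because the fix is free. Confidence in the size is medium, since the SD, the correlation and the test level are all assumed.

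**What to change.** Delete the rule that turns baseline differences into covariates, and keep the baseline comparison as description. State for Aim 1 that the WET–PE difference and its 95% interval at 10, 20 and 30 weeks come from one pre-specified direct-ML repeated-measures model (or an ANCOVA at each visit) that always includes baseline CAPS-5, and that this interval is compared with 10. Include gender because it is the randomisation factor, and site if wished; neither is expected to add much precision.

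The cost is SAP wording. Baseline CAPS-5, gender and site are already collected, and the planned Mplus software fits the model. No extra patients, visits or measures are needed.
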